By including a wider spectrum of patients with the target condition, the generalizability of the study findings will be greatly enhanced. Unpublished data from a sample of almost 70,000 members of Kaiser Permanente Southern California (KPSC) with incidentally detected pulmonary nodules indicate that nodules ≤ 10 mm make up 53% of the total population of patients with pulmonary nodules; by increasing the size threshold to ≤ 15 mm, we will include an additional 16% of the total nodule population. Even if as many as one third of the study patients with nodules measuring between 11 mm and 15 mm are not managed initially by CT

surveillance, and instead undergo an initial invasive biopsy or surgical procedure, this would still increase the size of the target population considerably and improve generalizability.

By increasing the size of the target population, we will also improve feasibility, both by casting a wider net that helps us to meet enrollment targets more efficiently, and by increasing the expected prevalence of cancer in the enrolled sample. Based on KPSC data, we estimate that 2% of patients with nodules measuring ≤ 10 mm will have a cancerous nodule, whereas 3% of patients with nodules measuring ≤ 15 mm will have a cancerous nodule (including almost 7% of patients with nodules measuring between 11 mm and 15 mm). Because the study is powered to demonstrate equivalence in stage distribution for patients with cancerous nodules, the increase in the expected frequency of cancer will enable us to meet our goals for sample size much more efficiently. Specifically, we anticipate that approximately 1,056 enrolled patients will have a cancerous nodule, which is greater than our initial estimate of approximately 900 patients. Of note, the original required sample size to achieve statistical power of 90% will not change, and the study will have slightly greater power than originally anticipated to demonstrate equivalence between the two comparison arms.

Finally, the proposed change will not introduce bias and therefore does not threaten validity, because both the more frequent and less frequent surveillance groups will include patients with nodules measuring ≤ 15 mm.

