To examine whether among participants with cancerous nodules, less intensive surveillance will be non-inferior to more intensive surveillance for the frequency of cancer progression beyond AJCC 7th edition stage T1a (or T1b for 8th edition) disease, we will use hierarchical logistic regression that includes random site effects to account for clustering of patients within sites and to capture institutional characteristics that are not explicitly modeled. Hierarchical logistic regression models will be fitted with and without adjusting for potential confounders including age, gender, ethnicity/race, smoking, body mass index (BMI), baseline nodule size, and any facility-level factors balanced during the randomization.

We will conduct a main analysis and several sensitivity analyses.

1. The main intent to treat analysis will include all enrolled participants in both study arms
2. A modified intent to treat sensitivity analysis will include:
 - a. For integrated healthcare systems, all active members
 - b. For other systems, patients who have at least one follow-up visit
3. On treatment sensitivity analyses will include those who met the definition of adherence to first recommended test and to overall surveillance protocol
4. We will conduct another sensitivity analysis using all nodules, instead of cancerous nodules, as the denominator to evaluate rates instead of proportions, given some concern about the potential for overdiagnosis in the more intensive arm. However, we are concerned about evaluating rates among all nodules due to the potential for differential enrollment of very small, likely insignificant nodules across sites. Inclusion of these nodules in overall rates will inflate the denominator without an increase in

numerator, resulting in smaller rates. Thus, we will evaluate variation in lung cancer rates across site within arms. Significant heterogeneity among the sites will provide evidence that the rates may be unreliable due to differential enrollment.

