adherence indicators and the surveillance arm will be obtained. To examine whether among all participants with a lung nodule ≤ 15 mm, more intensive surveillance will be associated with worse adherence to the surveillance protocol than less intensive surveillance, we will use hierarchical logistic regression that includes random site effects, with and without adjusting for potential confounders including age, gender, ethnicity/race, smoking, BMI, nodule size, and any facility-level factors balanced during the randomization.

Sample size and power calculations by aim

Preliminary data from a retrospective study of patients who underwent one or more chest CT scans at KPSC (2006-2012) showed that 76% of chest CT scans are performed in unique patients, and that approximately 30% of these individuals will have a prior history of cancer. Of the remainder, approximately 32% of unique patients (with no prior cancer diagnosis) who undergo chest CT will have a pulmonary nodule ≤ 30 mm, and 72% of all nodules measure ≤ 15 mm. Thus, we expect that approximately 16% of all unique patients who undergo chest CT will have a qualifying pulmonary nodule measuring ≤ 15 mm and no prior history of cancer. Data provided by participating sites indicates that more than 376,000 chest CT scans will be performed during the planned 20-month enrollment period in over 279,500 unique individuals (**Table 1**). This translates to an estimated target population size of approximately 45,000 patients with qualifying nodules. Allowing for site-level variation in the proportion of patients with a prior history of cancer and patients with nodules detected on prior chest CT scans, we will passively enroll a minimum of 35,200 individuals with a nodule ≤ 15 mm at one of the 14 health systems (24 individual study sites for cluster randomization) during the initial 28-month recruitment period. To allow time to complete the evaluation and accrue outcomes, patients will be followed for at least 2 years during the funding period. Among these individuals with small pulmonary nodules, we assume (based on data from KPSC) that 3.0% will be diagnosed with lung cancer, resulting in a sample size of approximately 1,056 patients with cancerous nodules.

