All subjects 35 years or older who have at least one newly identified pulmonary nodule measuring ≤15 mm detected on a chest CT conducted for any reason will be passively enrolled into the study. Exclusion criteria include subjects with a known extrathoracic cancer within the past 5 years. For sufficient power for establishing non-inferiority of the less intensive strategy, we estimate that we will need to identify 279,500 subjects who underwent chest CT to identify 35,200 subjects with small lung nodules of interest. Subjects with nodules will be identified by practicing radiologists, who will trigger an alert in the Radiology Information System (RIS) to embed a template with the recommended surveillance protocol into the dictated radiology report. In addition, sites will use manual and/or automated methods to search radiology reports and identify subjects with small nodules who may not have been enrolled, thereby allowing us to measure adherence at the level of the interpreting radiologist. Additional alerts flowing from the RIS to the Electronic Medical Record (EMR) will generate letters or emails to the ordering physician and patient notifying them of the results, explaining the results and the recommendation for follow-up, describing the study goals and duration, and specifying the types of data to be collected. Contact information for the project coordinator and Principal Investigator (PI) will be provided. An alert will also be created to send the radiology report to the local site data repository that will then be used by protocol coordinators to extract study outcome information through linkage with the internal health systems database and cancer registries. Patients will complete validated measures of anxiety, emotional distress and general health status via the Internet. Patient- and physician-level data will be exported to the central data repository at Data Coordinating Center.

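### The within-arm test of between-site cancer rates cannot tell selective enrolment from case mix, and it cannot see the between-arm enrolment difference that would bias the all-nodule analysis

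*Combined protocol and SAP*

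**What the plan says.** The main H1a analysis takes participants whose nodules prove cancerous as its denominator. Sensitivity analysis 4 under the H1a primary endpoint (Analysis Plan) repeats the comparison "using all nodules, instead of cancerous nodules, as the denominator to evaluate rates instead of proportions, given some concern about the potential for overdiagnosis". The arm where this is feared is the one with more frequent scans. The plan then worries that sites may differ in how readily they enrol very small, probably insignificant nodules, which would enlarge the denominator without adding events. Its response is: "Thus, we will evaluate variation in lung cancer rates across site within arms". The reading to be placed on the result follows: "Significant heterogeneity among the sites will provide evidence that the rates may be unreliable due to differential enrollment".

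No test, significance level, amount of variation or covariate adjustment is given for this check. The H1a hierarchical models are to be "fitted with and without adjusting for potential confounders including age, gender, ethnicity/race, smoking, body mass index (BMI), baseline nodule size"; they may also include the site characteristics balanced at randomization. The plan does not say whether the heterogeneity check uses those models. Individual mode of detection is not among the patient covariates listed.

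Two other places bear on the point. The section on the size threshold (Inclusion Criteria) puts the cancer rate at 2% for nodules up to 10 mm and 3% up to 15 mm, "including almost 7% of patients with nodules measuring between 11 mm and 15 mm". Human Subjects Involvement says sites will "search radiology reports and identify subjects with small nodules who may not have been enrolled", and Data Collection and Patient Enrollment provides for review of a sample of chest CT reports to confirm that eligible patients are enrolled.

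**The concern.** The check is meant to show whether the all-nodule rates can be trusted. It would need to respond to selective enrolment and to little else, and to respond to the kind of selective enrolment that distorts the treatment comparison. It does neither.

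**Other causes of the signal.** Table 1 shows sites that differ in type (safety net, referral, university, integrated), in endemic mycosis and in whether screening-detected nodules are enrolled. Cancer risk rises steeply with nodule size. All of these move a site's cancer rate without any selective enrolment.

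**The harmful pattern is invisible.** The comparison is biased when enrolment of tiny nodules differs between arms. A test run inside each arm does not look there. A between-arm difference is plausible: the trial is unblinded, the radiologist enrols by inserting text that carries the assigned recommendation, and Tables 2 and 3 differ for small incidental solid nodules.

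**What is at stake.** Cancer diagnosis occurs after randomization, and the plan itself allows that overdiagnosis may affect it. Extra small cancers in the more intensive arm would lower that arm's proportion above T1a. The all-nodule analysis is the only described analysis tied to that concern. A misleading check could discredit it wrongly or reassure wrongly about it.

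**Working it through.** The documents give no operating figure for this check, so there is none to reproduce. The counts behind it do reproduce: 35,200 × 0.03 = 1,056 cancers.

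**Inputs from the documents**
- Clusters: "24 individual study sites for cluster randomization". Table 1 gives 7 systems assigned More and 6 assigned Less; the 11 service areas of Kaiser Permanente Southern California bring the total to 24.
- Enrolment: "we will passively enroll a minimum of 35,200 individuals". 35,200 / 24 = 1,467 per site and 1,056 / 24 = 44 cancers per site, if sites are equal.
- Cancer rate: 2% up to 10 mm, about 7% at 11-15 mm.
- Share of 11-15 mm nodules among eligible nodules: 16 / (53 + 16) = 23%. Implied mean rate: 0.77 × 2% + 0.23 × 7% = 3.2%, close to the plan's 3%.

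**Assumptions**
- 12 equal sites per arm.
- Unadjusted Pearson chi-square test of equal rates across the sites of an arm, 11 df, 5% level (critical value 19.68).
- Share of larger nodules uniform across sites, over ranges centred near 23%.

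**Step 1, no true variation.** Each arm is flagged 5% of the time. At least one of two: 1 − 0.95² = 9.75%.

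**Step 2, size mix only.** Site rate = 2% + 5% × share. For a range of width w, the between-site SD is 5 × w / √12 points. The statistic behaves approximately as [1 + (n − 1) × ICC] × χ²(11), with ICC = SD² / [p(1 − p)].

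For a share of 13-33%:
- w = 0.20, SD = 0.29 points.
- ICC = 0.00289² / (0.0316 × 0.9684) = 0.00027.
- Inflation = 1 + 1,466 × 0.00027 = 1.40.
- P(χ²(11) > 19.68 / 1.40) = 23% in one arm.
- Either arm: 1 − 0.77² = 41%.

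Simulation gives nearly the same values, and repeat runs differ by a point or two:

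| Share of 11-15 mm nodules across sites | Site cancer rates | One arm | At least one arm |
|---|---|---|---|
| no variation | equal | 5% | 10% |
| 18-28% | 2.9-3.4% | 8-9% | 16% |
| 13-33% | 2.7-3.7% | 22% | 40% |
| 8-38% | 2.4-3.9% | 50% | 76% |

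Sites of 1,333 (after the 10% loss), a California-weighted layout and a strongly unequal layout change these by only a few points.

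**Step 3, all case mix together.** If the true between-site SD on a 3% mean is 0.25, 0.5, 0.75 or 1.0 points (assumed), at least one arm is flagged about 33%, 88%, 99% or 100% of the time. A 95% chance in at least one arm needs an SD of about 0.58 points.

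**Step 4, the enrolment difference that matters.** Every site in one arm enrols a fraction e of extra zero-risk nodules, so that arm's rate becomes 3% / (1 + e):
- e = 10%: 2.7%.
- e = 20%: 2.5%.
- e = 30%: 2.3%.

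The rate of tumours above T1a in that arm shrinks by the same factor, a relative fall of 1 − 1/1.1 = 9% up to 1 − 1/1.3 = 23%. All sites in the arm still share one rate, so the within-arm test is flagged in about 5% of simulations, its nominal error.

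**The case against.** Five points can be made for the plan.

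- **Nothing is discarded.** A reader might infer that a significant test decides the matter and removes the all-nodule analysis. The text does not support that. The analysis is unconditional, and heterogeneity is called only evidence that the rates may be unreliable. This stands.
- **Near-certain triggering is not shown.** A reader might also infer that the check will be significant almost every time. That needs a between-site SD of roughly 0.6 points or more. The documents give no between-site variation in cancer rates, and the ICC of 0.01 in the power section is for progression among cancers. With a narrow spread in size mix the chance is 16%. This stands.
- **The simulated test is assumed.** If heterogeneity were examined in the size- and smoking-adjusted model, much of the case mix would be removed. Also, 11 of the 24 clusters belong to one integrated system, so contrasts in setting do not apply among them. Both are fair, but the plan does not say that adjustment will be used for this check.
- **Looking within arms is sensible for cancer rates.** Comparing cancer rates between arms would mix enrolment differences with the overdiagnosis the analysis is meant to reveal. This is right. It means the between-arm comparison should use enrolment fractions and baseline size; it does not make the within-arm test informative about bias.
- **Safeguards exist.** Matching and re-randomization balance several site factors, and report sampling checks enrolment. Balance before enrolment does not prevent radiologists enrolling differently once the arm is known, and the plan does not link the report search to this analysis.

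**Conclusion.** The stated inference does not hold. Significant between-site heterogeneity is not specific to differential enrolment, and its absence says nothing about a difference between arms. Size mix alone raises the chance of a flag in at least one arm from about 10% to 16%, 40% or 76% over the ranges assumed, while a uniform 10-30% over-enrolment of zero-risk nodules in one arm is flagged at only the 5% error rate. The percentages rest on an unadjusted chi-square test, 12 equal sites per arm and assumed spreads in nodule size. The qualitative conclusion does not depend on them, except that full case-mix adjustment would weaken the first half.

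The point concerns how one sensitivity analysis is interpreted; the primary analysis is unchanged. It would be too strong to call the all-nodule analysis the only guard against overdiagnosis. The hypotheses also name all-nodule TNM stage and overall survival, although the survival analysis described under H1c is restricted to participants with cancerous nodules. The supportable statement is that it is the only described analysis the plan ties to overdiagnosis.

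**What to change.** In sensitivity analysis 4:

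1. Remove the statement that significant heterogeneity is evidence of differential enrolment.
2. State that the all-nodule analysis will always be reported, adjusted for baseline nodule size, smoking and mode of detection.
3. Assess differential enrolment by comparing, between arms and allowing for clustering, the enrolled-to-eligible fraction from the radiology report search already planned and the baseline size distribution of enrolled nodules.
4. Describe between-site variation in cancer rates after case-mix adjustment, as an estimate with an interval and without a significance trigger.
5. If wanted, add an analysis restricted to nodules of 6 mm or more, labelled supplementary. It removes a stratum in which the assigned protocols differ, so overdiagnosis arising there would be missed. Radiologists also have discretion over some larger nodules, for example those that look benign.

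The cost is a change of SAP wording and a small amount of extra analysis on data already planned. This assumes that the report search records nodule size and eligibility for patients who were not enrolled.

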The primary study objectives include, among individuals with small pulmonary nodules identified either incidentally or by screening, comparing more vs. less intensive CT surveillance for the progression of cancer beyond AJCC 7th edition stage T1a disease (or T1b in the AJCC 8th edition) (Aim 1), nodule-related emotional distress (Aim 2), health care resource utilization and exposure to diagnostic radiation (Aim 3), and overall adherence with the recommended surveillance protocol (Aim 4).

The secondary objectives include comparing more vs. less intensive CT surveillance for the timeliness of lung cancer diagnosis and overall survival of patients in each study arm who prove to have a cancerous nodule (Aim 1), patient general health status and satisfaction with the evaluation process and the provider satisfaction with the surveillance protocol and the evaluation process (Aim 2), and adherence to use of low radiation-dose techniques (Aim 4). In general, we hypothesize that more intensive follow-up will result in more CT imaging (by design), greater radiation exposure, more downstream testing, greater anxiety and emotional distress, slightly shorter times to cancer diagnosis, and worse adherence to follow-up, and no effect on cancer stage distribution or overall survival.

Primary endpoints:

Aim 1: Proportion of lung cancers that are greater than 20mm

- Measured as progression beyond AJCC 7th edition T stage of T1a or, equivalently, AJCC 8th edition T stage of T1b

Aim 2: Nodule-related anxiety and emotional distress at 1-2 months, 13-24 months, and ≥25 months after nodule identification

- Measured using the IES-R and STAI-6

Aim 3:

1. Health care resource utilization within 26 months following nodule identification
 - Number of visits within 26 months of nodule identification, including the following exams (separate analyses by type of exam):
 - Chest CT scans
 - Chest x-rays
 - PET or PET/CT scans
 - Biopsies (look separately and together): Bronchoscopic biopsy, percutaneous biopsy, surgical biopsy/resection, extrapulmonary biopsy.
 - We will not include any exams after the date of cancer diagnosis, but will include biopsy that led to the cancer diagnosis
2. Serious complications within 7 days and within 30 days of a chest CT, chest x-ray, PET or PET/CT scan, or biopsy (bronchoscopic biopsy, percutaneous biopsy, surgical biopsy/resection, extrapulmonary biopsy) performed within 26 months of baseline CT:
 - Pneumothorax

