H1a: Among participants with nodules that prove to be cancerous, less intensive surveillance will be non-inferior to more intensive surveillance for: (a) the frequency of cancer progression beyond AJCC 7th edition stage T1a disease (or T1b for AJCC 8th edition) and (b) the frequency of cancer progression beyond AJCC 7th edition TNM stage T1aN0M0 (or T1bN0M0 for AJCC 8th edition). In addition, among participants with *lung nodules*, less intensive surveillance will be non-inferior to more intensive surveillance for: (a) the frequency of cancer progression beyond AJCC 7th edition stage T1a disease (or T1b for AJCC 8th edition); and (b) the frequency of cancer progression beyond AJCC 7th edition TNM stage T1aN0M0 (or T1bN0M0 for AJCC 8th edition).. Furthermore, in exploratory analyses for HTE, we hypothesize that individuals who are most likely to benefit from more intensive surveillance will include older people, people with larger nodules (>8 mm), patients with solid or part-solid nodules (compared with non-solid

nodules), and individuals with nodules detected by screening (compared with individuals who have nodules that are incidentally detected).

H1b: Among participants with nodules that prove to be cancerous, more intensive surveillance will result in more timely diagnosis than less intensive surveillance.

H1c: Among participants with nodules that prove to be cancerous, less intensive surveillance will be non-inferior to more intensive surveillance for overall survival. Among participants with lung nodules, less intensive surveillance will be non-inferior to more intensive surveillance for overall survival.

H2a: Among all participants with a lung nodule ≤ 15 mm, more intensive surveillance will be associated with greater levels of emotional distress and state anxiety at 13-24 months, but levels of distress and anxiety similar to less intensive surveillance at 1-2 months and ≥ 25 months.

H2b: Among all participants with a lung nodule ≤ 15 mm, more intensive surveillance will be associated with scores similar to less intensive surveillance for general health status at 1-2 months, 13-24 months and ≥ 25 months.

H2c: Among participating radiologists and pulmonologists, satisfaction with the surveillance protocol will be greater among those who practice at institutions assigned to the less intensive protocol.

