5. We will perform additional sensitivity analyses to test the robustness of findings to the source of data. The primary analysis will include data from all three sources (local and state tumor registries and electronic health records). The first sensitivity analysis will be limited to lung cancer outcomes from both state and local tumor registries, truncating follow-up time as necessary to ensure non-differential follow-up across sites (likely at a minimum of 17-18 months). Another sensitivity analysis will be limited to lung cancer outcomes from only state registries, truncating follow-up as per above.
6. A separate analysis will examine patients who adhere to the recommendations for evaluation compared to those who do not, within each of the two study arms and for both arms combined, for the primary outcome of tumor (T) stage >AJCC 7th edition stage T1A (or AJCC 8th edition stage T1b).

H1a - Secondary endpoint:

TNM stage: We will conduct a secondary analysis to compare the presence of AJCC-7 TNM stage >T1aN0M0 or AJCC-8 TNM stage >T1bN0M0 between study arms. This is a secondary analysis because it is not possible to ascertain TNM stage at the time of nodule identification, so we will not be able to compare rates of progression for this outcome. Nevertheless, we will be able to make an unbiased comparison of the presence of TNM stage >T1aN0M0 at the time of diagnosis. Because it is possible that a small percentage of enrolled patients will have minimal or occult N1-3 and/or M1 disease at the time of enrollment, the baseline risk using this outcome definition will be greater than what we assumed for the primary outcome of tumor (T) stage >T1a, and therefore we will have less power to show non-inferiority in this sensitivity analysis.

H1b - Secondary endpoints:

Timeliness of diagnosis: To investigate whether among participants with cancerous nodules, less intensive surveillance will be non-inferior to more intensive surveillance for timeliness of diagnosis, we will restrict our analysis to participants with cancerous nodules and use Cox regression models where time from initial nodule identification to diagnosis is the outcome variable.

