Timeliness of treatment: To investigate whether among participants with cancerous nodules, less intensive surveillance will be non-inferior to more intensive surveillance for timeliness of treatment, we will restrict our analysis to participants with cancerous nodules and use Cox regression models where time from initial nodule identification to treatment is the outcome variable. Patients who die or do not receive treatment will be censored at end of follow-up. We will consider using competing risk models, as necessary.

H1c: Secondary endpoint

Survival: To investigate whether among participants with cancerous nodules, less intensive surveillance will be non-inferior to more intensive surveillance for overall survival, we will restrict our analysis to participants with cancerous nodules and use Cox regression models where time from initial nodule identification to death as the outcome variable. Patients will be censored at end of follow-up.

For all time-to-event analyses, clustering by site will be handled by specifying subjects nested within each cluster and using robust sandwich estimators for statistical inferences.⁶¹ The proportionality assumption will be checked by creating log-minus-log plots. To explore whether individuals who are most likely to benefit from more intensive surveillance, subgroup analyses will examine the effect of age (using the median and/or quartile values as cut points), nodule size (>8 mm), nodule attenuation (solid or part-solid nodules compared with non-solid nodules), and mode of detection (detected by screening compared with incidentally detected).

Analytically, we will include interaction terms between each of these factors with treatment in the models, respectively. For significant interactions, we will also conduct subgroup analysis to explore the treatment effects in corresponding subgroups. Since the study is not powered to test interaction terms, these analyses will be exploratory. For H1b, to study whether among participants with cancerous nodules, more intensive surveillance will result in more timely diagnosis and treatment than less intensive surveillance, we will adopt similar strategy used for comparing overall survival described above.

H2a:

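### For timeliness of diagnosis and treatment the plan states both superiority of more intensive and non-inferiority of less intensive surveillance, unordered and with no margin

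*Combined protocol and SAP*

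**What the plan says.** All of this is in the combined document, under Statistical Considerations and Data Analysis.

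- **Objectives.** The general expectation for more intensive follow-up includes "slightly shorter times to cancer diagnosis, and worse adherence to follow-up, and no effect on cancer stage distribution or overall survival".
- **Hypotheses, H1b.** Among participants with cancerous nodules, "more intensive surveillance will result in more timely diagnosis than less intensive surveillance". Only diagnosis is named. The list of secondary endpoints has both time to diagnosis and time to treatment.
- **Analysis Plan, H1b, timeliness of diagnosis.** The aim is to investigate whether "less intensive surveillance will be non-inferior to more intensive surveillance for timeliness of diagnosis", and for this "we will restrict our analysis to participants with cancerous nodules and use Cox regression models".
- **Analysis Plan, H1b, timeliness of treatment.** The aim is to investigate whether "less intensive surveillance will be non-inferior to more intensive surveillance for timeliness of treatment", again by Cox regression.
- **Analysis Plan, paragraph on all time-to-event analyses (after H1c).** Clustering by site is handled "using robust sandwich estimators for statistical inferences". The paragraph closes by returning to H1b, to study whether "more intensive surveillance will result in more timely diagnosis and treatment than less intensive surveillance", and says that "we will adopt similar strategy used for comparing overall survival described above". The survival analysis it points to is framed as non-inferiority, also without a margin.
- **Sample size and power calculations, Aim 1.** The only quantified difference is 5 percentage points in tumor progression, for the primary outcome. Timeliness has no margin, power or sample size.

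**The concern.** A superiority hypothesis and a non-inferiority hypothesis need different decision rules. Superiority of more intensive surveillance is judged against HR = 1. Non-inferiority of less intensive surveillance is judged against a margin fixed beforehand, using a confidence bound. The plan names both objectives for the same two endpoints, gives no order, and supplies no rule for the second.

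The interpretation is therefore open. If diagnosis is significantly later under less intensive surveillance, H1b is supported. If the difference is not significant, a report could say that the non-inferiority objective was met, although failing to show a difference is not evidence of non-inferiority. Timeliness is one of the outcomes the protocol describes as important to patients, so a reader should be able to tell beforehand which claim the trial is entitled to make.

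**Working it through.** **1. Does the plan's one Aim 1 margin carry over?** First reproduce the primary calculation. Inputs from the Aim 1 power paragraph: 5% progression, 5-point difference, two-sided alpha 0.05, ICC 0.01, 888 cancers. The sample size section gives 24 randomized units.

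- Cluster size 888/24 = 37; design effect 1 + 36 × 0.01 = 1.36; effective n per arm 444/1.36 = 326.5.
- SE = √(2 × 0.05 × 0.95/326.5) = 0.01706.
- Power = Φ(0.05/0.01706 − 1.96) = Φ(0.971) = 0.834. The plan states 0.83.

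The figure reproduces as a non-inferiority calculation with a 5-point margin. Treating the same inputs as a 5% versus 10% superiority test gives only about 0.68. The primary outcome therefore has a usable margin. That margin is an absolute difference in a proportion and does not translate into a hazard ratio for time to diagnosis or treatment.

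**2. Which objective do the texts support?** Superiority appears in the Objectives, in H1b (diagnosis) and at the end of the time-to-event paragraph (diagnosis and treatment). Non-inferiority appears in the two H1b endpoint paragraphs. Nothing ranks one above the other.

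**3. How much depends on the missing margin?** This is an illustration only: the plan gives no margin, so a range is assumed. HR compares less with more intensive surveillance for the rate of diagnosis; below 1 means later diagnosis under less intensive. Further assumptions: 960 diagnosis events (the plan's anticipated cancers for Aim 1), equal arms, 24 equal clusters, two-sided 95% intervals. The ICC is varied because 0.01 is stated for the binary primary outcome, not for a Cox analysis.

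- SE(log HR) = 2/√(960/DE), with DE = 1 + 39 × ICC. ICC 0: DE 1, SE 0.0645. ICC 0.01: DE 1.39, SE 0.0761. ICC 0.05: DE 2.95, SE 0.1109.
- More intensive superior if observed HR < exp(−1.96 × SE).
- Less intensive non-inferior if observed HR > margin × exp(1.96 × SE).

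| Rule | ICC 0 | ICC 0.01 | ICC 0.05 |
|---|---|---|---|
| Superiority: HR below | 0.881 | 0.861 | 0.805 |
| Non-inferiority, margin 0.90: HR above | 1.021 | 1.045 | 1.118 |
| Margin 0.85 | 0.965 | 0.987 | 1.056 |
| Margin 0.80 | 0.908 | 0.929 | 0.994 |
| Margin 0.75 | 0.851 | 0.871 | 0.932 |
| Margin 0.70 | 0.794 | 0.813 | 0.870 |

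Take an observed HR of 0.87:

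- ICC 0: superior and non-inferior at margin 0.75; superior only at 0.80.
- ICC 0.01: neither at 0.75; non-inferior only at 0.70.

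At a true HR of 1 with ICC 0.01, non-inferiority power is 28.2%, 57.0%, 83.5% and 96.6% for margins 0.90, 0.85, 0.80 and 0.75. The verdict on timeliness turns on a number that the plan does not contain.

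**The case against.** The strongest reply is that the superiority analysis is already in the plan. It stands in the objectives, the hypothesis and the closing time-to-event paragraph, so the non-inferiority sentences may simply be wording carried over from H1a. Both framings use the same Cox model and site-robust variance, and would give the same HR and interval. This stands in part: it would be wrong to say that the plan tests only non-inferiority. But the non-inferiority aim appears in two separate paragraphs under the H1b heading, and the text does not tell a reader which governs.

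Three stronger readings are tempting, and the documents do not support them.

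- **The two claims exclude each other.** They need not. A small delay can be statistically significant and still lie inside a wide margin, as the HR range 0.813 to 0.861 shows at margin 0.70 with ICC 0.01.
- **The endpoint cannot fail.** Nothing in the plan says a non-significant difference will be reported as non-inferiority; that would be a prediction of misreporting. Without a margin the claim is untestable, which is not automatic success. With a margin, some results would meet neither rule (HR 0.881 to 0.908 at margin 0.80, no clustering).
- **The chance of a non-significant result measures the harm.** At a true HR of 0.90 with ICC 0.01 that chance is 1 − 0.282 = 72%. This is the type II error of the superiority test, and it is the same after the fix.

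It is also fair to say that non-inferiority suits the trial's wider question of whether less intensive surveillance is acceptable. Keeping it is defensible, provided a margin and an order are given.

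**Conclusion.** The point holds in this form: for time to diagnosis and time to treatment the plan states two unordered objectives, one of which has no margin or confidence-bound rule and so cannot be tested as written. A non-significant difference could be read as meeting it.

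The size is limited. The endpoints are secondary, the primary conclusion is unaffected, and the estimated HR and its interval do not change. What changes is the claim that may be drawn from them. That the plan has two objectives and no margin rests on the text alone. The HR thresholds are illustrative and rest on assumed margins, about 960 events, equal arms and clusters, and an assumed ICC. For treatment the event count may be lower, since untreated patients are censored.

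**What to change.** In the H1b paragraphs of the Analysis Plan, replace the two non-inferiority sentences with the superiority comparison: Cox model with site-robust variance, HR with 95% CI, two-sided 0.05. Add treatment to H1b in the Hypotheses list. State that no non-inferiority claim will be made for timeliness.

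If the sponsor prefers to keep non-inferiority, state a justified HR margin for each endpoint, the confidence level, and its order relative to superiority. Disclose whether outcome data had been seen when these were set.

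The cost is a wording amendment, with no new data or analysis. The timing needs a sentence of its own. The version table dates the current version 7-21-25, while the Aim 1 outcomes section allotted May 1, 2022 to January 31, 2023 for linkage, cleaning and analysis. The documents do not show whether results were known. If they were, a margin chosen now would be post hoc, which favors the superiority wording, and the choice of objective should be disclosed in either case.
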